The use of mobile devices has the potential to improve the delivery of cost-effective, high-quality, standardized surveillance of cancer survivors. In contrast to other medical subspecialties, long-term survivorship research on post-surgical patients using mobile devices has been uncommon. This study proposes to develop and test a novel web-based mobile technology for surveillance of cancer survivors following surgery for bone metastases. The study will focus on three aspects of feasibility of the proposed new approach: adaptation, limited efficacy testing, and acceptability.⁸⁴ The potential economic impact includes cost savings for both patients and providers. The potential impact on survivorship care is to optimize the frequency and fidelity of outcomes research needed for the aging cancer survivor following skeletal surgery.¹⁸

The optimal surveillance system that preserves patient privacy, preserves overall fidelity, minimizes cost, and allows for requisite data quality has not yet been identified [5, 16, and 17]. In this

PI: [name], PhD

Protocol: 2015-0966

August 21, 2018

study, we propose to use mobile devices to enhance the regular postoperative surveillance of cancer patients, all of whom have undergone intramedullary fixation for cancer metastases in the bone.

3.0 Patient Eligibility:

Patients will be eligible to participate in this study if they:

- Have been scheduled for an Intramedullary nailing (IM) surgery with the department of Orthopaedic Oncology at UT MD Anderson Cancer Center.
- Are able to read and write English.
- Are 18 years or older.
- Are willing and able to use a smartphone or tablet comfortably.
- Have access to mobile hot spot, wireless internet, and/or cellular service.
- Must have a caregiver or assistance at home who can assist with collecting PT measures.

Exclusion Criteria:

- None

4.0 Research Plan and Methods:

The objectives for this protocol will be achieved in multiple steps to ensure patient safety. There are six outcome measures, including one that is completed by the patient, two by the clinician, and three assessed by the physical therapist (see **Outcomes** section below).

Outcomes

Functional outcomes and quality of life will be assessed in this study via the following instruments:

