For Specific Aim 1, the mobile device APP used in this study will be developed by the collaborator (e-Health Technology Program). For objective 1 (Specific Aim 2), we will assess the feasibility of mobile device surveillance by comparing whether similar measurements are obtained using the mobile device format versus the established face-to-face format when performed during the same appointment on the same patient. A group of 10 patients who meet the inclusion criteria and have completed the informed consent process will be evaluated by the treating physician and physical therapist face-to-face at the normally scheduled clinic visits (2, 6, 12 and 24 weeks after surgery). After seeing the physician, the patient will then use a mobile device (provided to them with assistance and training from the study coordinator) while still at the clinic for outcome assessment videos. The mobile device data will be provided to independent evaluators (a physician and a

PI: [name], PhD

Protocol: 2015-0966

August 21, 2018

physical therapist who are different from the physician and the physical therapist performing the face-to-face evaluation). The independent evaluators will not have a face-to-face visit with the patient and will use the video sequences to assess the same functional outcomes (MSTS, ECOG, TUG, EVGS, FSST, NIH PROMIS GH).

For feasibility, we are looking for inter-rater agreement on the physician assessed score (defined as less than 10% difference between MSTS scores evaluated using video v face-to-face) for a minimum number of patients (in this step, the MSTS score agreement for a minimum of 70% of the patients. If the feasibility criterion has been met, the research team will move forward to the limited efficacy testing. If feasibility criteria has not been met, the research team will identify the limitations and modify the process, enroll an additional 10 patients and repeat the feasibility assessment.

Specific Aim 3: Limited Efficacy Testing

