Once the adaptation of the face-to-face follow-up to the mobile format has been verified, we will move to the limited efficacy testing (Objective 2/Specific Aim 3). A group of 40 patients that fit the inclusion criteria and have completed the informed consent process will be enrolled in the study. Participants will be enrolled in either a control group (n=20) or to the mobile surveillance group (n=20). The control group will have face-to-face follow up visits with no mobile surveillance at the appropriate time points. The mobile surveillance group (n=20) will have both face-to-face visits and additional data obtained using mobile devices. Patients in both groups will complete the same set of outcome measures. These measures will be administered at the following time points, 2, 6, 12, and 24 weeks.

Patients in the mobile surveillance group will complete an assessment using a mobile device at home during the week after their scheduled clinic visit at 2, 6, 12 and 24 weeks (see **Table 1** below). The mobile device data is in addition to data gathered at face-to-face clinical appointments, thereby adding outcome data and enhancing surveillance overall. Participants in the mobile surveillance group will take videos using the mobile devices and upload the data over the encrypted network using the My MD Anderson secure email transmission. Participants will be provided with a mobile device (or tablet) that is enabled with a mobile hot spot for data transmission. For recovery of function, video sequences will be acquired by patients performing prescribed tasks that will be used to quantify functional status according to the MSTS, ECOG, TUG, EVGS, FSST, NIH PROMIS GH Score. The participant's surgical wound will also be photographed using the mobile device. Quality of Life questionnaires and PROMIS SF v1 (Appendix G) surveys will be sent to the group for completion on their mobile device via REDCap Software or thru My MD Anderson email.

To ensure patient safety, participants in the mobile surveillance group will also engage in videoconferences at the prescribed timepoints using Vidyo or Zoom. All patient communication will be documented as follow-up notes in Clinic Station by the clinician.

Table 1. Study Design

Control Group n = 20	Mobile Surveillance Group Patients n = 20
Postoperative clinic visits	Postoperative clinic visits
2 weeks	2 weeks
6 weeks	6 weeks
12 weeks	12 weeks
24 weeks	24 weeks
Measures:	Measures:
Completion rates	Completion rates

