Patients will be approached for participation for this study at their clinic visit. Potential subjects will be informed of their eligibility and asked if they would be interested in research participation. In the privacy of the exam room, surgeons and/or research nurse or research data coordinator will discuss all aspects of the study with potential subjects and answer any questions. Interested subjects will then be given the informed consent documents and will have enough time to read over and ask questions. Subjects will be given a copy of the informed consent and will be further instructed about the study and the elements of the consent document. The research staff and/or attending physician will be available to address any questions or concerns the subject may have. Subjects who agree to participate will sign the protocol-specific informed consent.

A research nurse, research data coordinator, or PI designee with appropriate training and experience sufficient to address issues raised by potential subjects may obtain the Informed Consent. Patients may withdraw from the study at any time. Once the patient has consented for the study, he or she will be trained on how to use the mobile device or tablet.

Once a patient has been assigned to group 2 in both the feasibility and limited efficacy phases, he/she will be trained in clinic on how to use the app for both videos and photographs by a licensed Physical Therapist. Reference guides and instruction manuals will be provided to the patient and contact information for the research team for any further assistance. The training session should take approximately 10-15 minutes per individual.

6.0 Statistics:

Feasibility Assessment

The feasibility assessment will consist of a group of 10 patients who meet the inclusion criteria. For feasibility, we are looking for inter-rater agreement on the physician assessed score (defined as less than 10% difference between MSTS scores evaluated using video v face-to-face) for a minimum number of patients (in this step, the MSTS score agreement for a minimum of 70% of the patients). If the feasibility criterion has been met, the research team will move forward to the limited efficacy testing. If feasibility criteria has not been met, the research team will identify the limitations and modify the process, enroll an additional 10 patients and repeat the feasibility assessment.

Limited Efficacy Testing

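### The only video versus face-to-face agreement test uses in-clinic recordings with an unspecified amount of staff help, so passing it does not verify the home recordings used next

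*Combined protocol and SAP*

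**What the plan says.** Section 4.0 (Specific Aim 1 and 2) compares the mobile format with face-to-face scoring "when performed during the same appointment on the same patient". At each of the four postoperative visits, after the face-to-face evaluation, "the patient will then use a mobile device (provided to them with assistance and training from the study coordinator) while still at the clinic". An independent physician and physical therapist then score the videos.

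Section 6.0 (Feasibility Assessment) sets the rule. The group is 10 patients. Agreement is "defined as less than 10% difference between MSTS scores evaluated using video v face-to-face", and the requirement is "the MSTS score agreement for a minimum of 70% of the patients". If the rule is not met, the process is modified and 10 more patients are enrolled.

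Section 4.0 (Specific Aim 3) reads a pass as follows: "Once the adaptation of the face-to-face follow-up to the mobile format has been verified, we will move to the limited efficacy testing". In that phase the 20 mobile-group patients "will complete an assessment using a mobile device at home during the week after their scheduled clinic visit", and the videos they take and upload are the source for the functional scores. Section 3.0 makes home help an entry condition: "Must have a caregiver or assistance at home who can assist with collecting PT measures".

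Specific Aim 3 in Section 1.0 promises a comparison of mobile with face-to-face data. Section 6.0 (Limited Efficacy Testing) defines two measures for the phase, completion and satisfaction. It gives no agreement measure, threshold or scorability check for home recordings.

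**The concern.** Objective 1 is about adapting follow-up to remote use. What makes it remote is the home setting, a lay helper and the absence of staff. The step that decides whether the format works includes none of these by design. It takes place in clinic, staff support is available, and the caregiver required by Section 3.0 has no stated role in it. Because help is neither limited nor recorded, a reader of the results could not tell whether the agreement belongs to recordings that patients can make alone.

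At stake is the pilot's feasibility claim. The format could be called verified with no same-appointment evidence that unaided recordings can be scored or agree with face-to-face scores. The planned repair loop is triggered only by failure of the in-clinic rule, so a problem that appears only at home would emerge after it. Completion would not reveal inaccurate scores, because it asks only whether MSTS, TUG and PROMIS are documented.

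**Working it through.** **The two steps side by side**

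| | Feasibility step | Limited efficacy step |
|---|---|---|
| Where recorded | Clinic | Home |
| Help | Coordinator; extent not stated | Caregiver or other helper |
| Gap from face-to-face score | Same appointment | Up to about a week |
| Planned recordings | 10 × 4 = 40 (a further 40 if a second group is enrolled) | 20 × 4 = 80 |
| Agreement rule | MSTS, less than 10%, at least 70% of patients | None in Section 6.0 |

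The documents do not say how the four visits of one patient combine into agreement for that patient, so 40 is the number of recordings planned, not necessarily the number that count.

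**The plan's own figures.** Section 6.0 gives no operating characteristic for the feasibility rule. Its only precision figures are the 95% half-widths at 20 per group, and both reproduce:
- Single rate: 1.96 × √(0.25/20) = 0.219 (stated 0.22).
- Difference, 0.50 versus 0.70: 1.96 × √(0.25/20 + 0.21/20) = 0.297 (stated 0.30).

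Neither bears on agreement.

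**How the pass rule depends on the recording conditions.** Inputs from the plan are n = 10 and a threshold of 7 (70% of 10). True patient-level agreement p is not given and is assumed. The chance of passing at the first attempt is

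P(X ≥ 7) = Σ (k = 7 to 10) C(10,k) p^k (1−p)^(10−k)

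| Assumed p | k = 7 | k = 8 | k = 9 | k = 10 | P(pass) |
|---|---|---|---|---|---|
| 0.85 | 0.130 | 0.276 | 0.347 | 0.197 | 0.95 |
| 0.80 | 0.201 | 0.302 | 0.268 | 0.107 | 0.88 |
| 0.70 | 0.267 | 0.233 | 0.121 | 0.028 | 0.65 |
| 0.65 | 0.252 | 0.176 | 0.072 | 0.013 | 0.51 |

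Take 85% as agreement with help. If unaided agreement is also 85%, nothing is lost. At 80% the chance of passing would fall by 0.07, at 70% by 0.30 and at 65% by 0.44. More basically, home agreement does not enter the rule at all, so the chance of passing stays the same whatever home agreement is.

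**What the data already planned could show.** One agreement result per patient from the 20 mobile-group patients would give, for an observed 14/20 (70%), an exact 95% interval of 45.7% to 88.1%. For comparison, an observed 7/10 in the feasibility step has an interval of 34.8% to 93.3%. The home estimate would be imprecise, but no worse than the one on which the phase opens.

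**The case against.** The staging is deliberate and sensible for a pilot. The first step isolates one question, whether an independent rater can score from video, with no time gap to confuse it. The second step moves to the home. This stands, and it is why the point concerns what a pass may be taken to show and not whether the first step should exist.

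Four stronger readings are tempting, and the documents do not support them.

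- *Staff make the recordings, or help at every visit.* Section 4.0 names the patient as the user, and the parenthesis describes how the device is provided. The extent of help is unstated, which is the problem. Section 5.0 also provides training by a physical therapist, reference guides and a team contact. These make good home recordings more likely but are not evidence of agreement.
- *The 3-meter course and the timing of the walk undermine the pass rule.* Those belong to TUG, and the rule uses MSTS alone. Of the six lower-extremity MSTS items, walking ability and gait pattern are the most plausibly sensitive to filming. Pain and emotional acceptance are much less so.
- *The home phase can say nothing about agreement.* The mobile group yields up to 80 clinic and home pairs. A gap of up to a week mixes recording error with recovery, so the pairs are imperfect, but they are informative. What is missing is a stated analysis.
- *The second phase is invalid if the first was too optimistic.* Its measures are completion and satisfaction, the home data are additional to clinic data, and videoconferences cover safety. Those measures do not depend on agreement.

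**Conclusion.** The point holds in a limited form. The only agreement test is made in clinic, with help that is neither bounded nor recorded. Passing it is described as verifying the mobile format, and the home recordings that follow have no prespecified agreement or scorability analysis despite Specific Aim 3. A pass supports scoring from video recorded in clinic. It leaves open whether patient and caregiver can produce scorable, agreeing recordings at home.

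The size is unknown, because the documents give no agreement figure with or without help. The contrast of 0.95 with 0.88, 0.65 or 0.51 rests on an assumed 85% with help and assumed losses of 5, 15 and 20 percentage points. It treats patients as independent and counts the first attempt only. It should not be read as a forecast. The pilot can run as planned, and the change is an inexpensive improvement that brings the claim into line with the evidence.

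**What to change.** 1. **Section 4.0, feasibility step.** After training and the first recording, have the patient, with the caregiver where present, record from the reference guide without staff help at the later feasibility visits. The coordinator stays for safety and logs any help given. Report MSTS agreement and the share of scorable recordings for the unaided recordings, each against the face-to-face score of the same visit. Recovery does not bias that estimate, because both scores come from one appointment. Do not interpret a difference between assisted and unaided recordings as the effect of help, because it is confounded with time since surgery and practice.
2. **Section 6.0, Limited Efficacy Testing.** Add a descriptive analysis of the mobile group's home recordings: the share that can be scored, and MSTS agreement with the preceding clinic visit under the existing 10% definition, with confidence intervals. State that a gap of up to a week mixes recording error with recovery.
3. **Section 4.0, Specific Aim 3.** Limit the statement that the format has been verified to in-clinic recordings.

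The cost is wording, one yes/no field for help per recording, and an analysis of data already collected. No visits, staff or patients are added. The downsides are that a few recordings may not be scorable (itself feasibility information) and that the rule may be somewhat harder to pass. The 2-week unaided recording and the home setting also remain untested at the same appointment.

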The preoperative and postoperative care for these patients is standardized. The surgical procedure is minimally invasive, performed through 3-4 small incisions, usually no larger than 3cm each. The hospital inpatient recovery is typically for 3-5 days, with regular scheduled postoperative visits at 2-3, 6-7 weeks, and 12-14 weeks from surgery. The timing of this first visit is specified so that a decision can be made as to whether the patient can proceed with additional treatment, such as radiation to the operated extremity, or chemotherapy. The key parts of this assessment include inspecting the surgical wounds for signs of infection and assessing the adequacy of soft tissue healing. In addition, the radiographic studies (x-rays) of the extremity are viewed by the physician. The time required for a surgeon to make this assessment for uncomplicated cases is typically short, averaging 5-7 minutes.

The post-operative follow-up visit utilizes standardized tools to establish patient-centered outcome data with a direct impact on the individual survivor as well as contributing to a dataset for predicting functional outcomes for all bone cancer survivors. However, only one-third of those seen are from local areas, and surveillance of persistent, late effects following surgery is suboptimal. Numerous obstacles limit both the patients' ability to attend face-to-face appointments (cost of travel, impaired mobility), and the providers' ability to collect patient-centered outcome data (clinic capacity). At our clinic, data show that approximately 30% of our patients miss an appointment in the post-operative period. A missed follow-up appointment prevents medical intervention needed to enhance survivorship and reduces data collection, which in turn, makes it difficult to accurately predict outcomes over time for future bone cancer survivors.

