There are two measurements for limited efficacy testing, completion rate and patient satisfaction/acceptability. Among the set of questionnaires the patients need to complete, MSTS,

PI: [name], PhD

Protocol: 2015-0966

August 21, 2018

TUG, and PROMIS are considered the most important. A patient is considered having completed the follow-up assessment if the three outcomes are documented for the 2-, 6-, 12, and 24-week evaluations. We will then report the completion rates for each group for comparison.

We will report the patient satisfaction rate using patient satisfaction surveys for both the control and the study groups. When the sample size is 20, a two-sided 95% confidence interval (CI) for completion rate or satisfaction rate using the large sample normal approximation will extend at most 0.22 from the observed rate (nQuery Advisor 7.0). When the sample size in the group is 20, the 95% CI will extend 0.30 from the observed difference in rate assuming the rate is 0.50 for one group and 0.70 for the other group. The physician satisfaction rate for using mobile devices will be reported. We will also address the economic impact for using mobile devices. Repeated measures analysis may be utilized to evaluate change over time in the completion status or questionnaire scores for each method.

7.0 Data Management and Security:

All patient-reported and task performance outcomes and clinical data (including videos/photos) gathered under this protocol will be stored in a password-protected database. Data will not be transferred to laptop computers that are removed from the institution. Identifiers (name, medical record number) will be collected but will be replaced by study numbers in the analytic file. The key linking these numbers will be retained in a locked file by the investigator.

Data (including videos/photos) using mobile devices or tables will be encrypted by the IT department securely transferred using MY MD Anderson secure email to the research team.

Only MDACC personnel designated by the Principal investigator will have access to study records/data. These personnel will be fully trained to maintain the confidential nature of the patient health information. Paper records will be stored in locked files inside a locked office. External storage will be password protected.

Study data will not be shared with any individuals or entities that are not involved in the study. These data will be used only for research purposes and for this research study.

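### No rule is given for allocating the 40 limited-efficacy patients to control or mobile surveillance, although completion and satisfaction are reported by group with a CI for the difference in rates

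*Combined protocol and SAP*

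**What the plan says.** Section 4.0 (Specific Aim 3: Limited Efficacy Testing) enrols 40 patients: "Participants will be enrolled in either a control group (n=20) or to the mobile surveillance group (n=20". Table 1 repeats the two group sizes. Neither says how a patient comes to be in one group or the other.

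The only other wording on allocation is in section 5.0 (Informed Consent), on device training: "Once a patient has been assigned to group 2 in both the feasibility and limited efficacy phases". Group 2 is not defined. The sentence also applies it to the feasibility phase, which section 4.0 (Specific Aim 1 and 2) describes as a single group: "A group of 10 patients who meet the inclusion criteria and have completed the informed consent process".

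Section 6.0 (Statistics, Limited Efficacy Testing) then sets out what is reported:

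- "There are two measurements for limited efficacy testing, completion rate and patient satisfaction/acceptability"
- Completion: "We will then report the completion rates for each group for comparison"
- Satisfaction: "We will report the patient satisfaction rate using patient satisfaction surveys for both the control and the study groups"
- Precision of the contrast, at assumed rates of 0.50 and 0.70: "When the sample size in the group is 20, the 95% CI will extend 0.30 from the observed difference in rate"

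Section 6.0 mentions no randomisation, alternation, matching, stratification, concealment or baseline adjustment. The one reference to a random process in the document is the date shifting for de-identification in section 7.0.

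**The concern.** A plan that states the precision of a between-group difference should say how the groups are formed. Without a rule, the plan can be followed exactly as written while patients or staff decide the group.

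The protocol itself names factors that could then act on both the group and the outcome. Section 2.0 gives travel cost and impaired mobility as obstacles to attendance and reports that "approximately 30% of our patients miss an appointment in the post-operative period". Completion under section 6.0 needs MSTS, TUG and PROMIS documented at all four time points, so the same obstacles bear on it. If they also influenced who entered which group, a difference in completion or satisfaction, or the absence of one, could reflect the patients rather than the mobile format. The direction could be either way, and the confidence interval would not show it.

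**Working it through.** **Inputs.** 20 patients per group (section 4.0 and Table 1). Rates 0.50 and 0.70 and half-widths 0.22 and 0.30 (section 6.0). About 30% of clinic patients missing an appointment (section 2.0), used only in step 4 and only as an assumption.

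**Step 1: reproduce the plan's precision.**

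- One group, worst case: 1.96 × sqrt(0.50 × 0.50/20) = 0.219. The plan says at most 0.22.
- Difference: 1.96 × sqrt(0.50 × 0.50/20 + 0.70 × 0.30/20) = 1.96 × 0.1517 = 0.297. The plan says 0.30.

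Both figures reproduce. They depend only on the group size and the rates, so naming an allocation method changes neither. For the same reason they say nothing about selection.

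**Step 2: look for an allocation rule.** Section 4.0 gives enrolment into one of two groups and section 5.0 gives assignment. Neither says by what method, by whom or when. Assignment cannot be read as implying a method, because the same sentence applies it to the feasibility phase, where section 4.0 describes no second group.

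**Step 3: sensitivity of the contrast.** Exchange one patient who would not complete in either group for one who would. Each group's rate moves by 1/20 = 0.05, in opposite directions, so the difference moves by 0.10.

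- Two exchanges: 2 × 0.10 = 0.20, which is the whole difference assumed in the plan's calculation (0.70 − 0.50).
- Three exchanges: 3 × 0.10 = 0.30, which is the planned half-width.

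**Step 4: illustration only.** Assume that the 30% missed-appointment figure is the share of non-completers, 0.30 × 40 = 12, and that the mobile format has no effect.

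- Split 6:6: 14/20 v 14/20, that is 0.70 v 0.70, difference 0.
- Split 9:3 (three exchanges): 11/20 v 17/20, that is 0.55 v 0.85, difference 0.30. SE = sqrt(0.55 × 0.45/20 + 0.85 × 0.15/20) = 0.137. 95% CI = 0.30 ± 0.268, or 0.03 to 0.57.

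Under 1:1 randomisation the number of non-completers in one group is hypergeometric (40 patients, 20 drawn), and the mean difference is zero. The probability of a difference of at least 0.30 in either direction is:

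| Assumed non-completers of 40 | Probability |
|---|---|
| 8 (20%) | 0.044 |
| 12 (30%) | 0.082 |
| 16 (40%) | 0.105 |

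So chance alone can produce such a split under randomisation, but with a known and small probability. With an unstated rule, that probability cannot be calculated.

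**The case against.** The strongest reply is that this is a pilot whose primary objective is feasibility. The only decision rule is MSTS agreement in the feasibility group. Section 6.0 gives rates and intervals for the limited efficacy phase, with no test and no go/no-go rule on the group contrast. A descriptive pilot may use a non-random allocation. All of that stands, and it limits the harm. It does not excuse leaving the allocation unstated when rates are set against each other.

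Other parts of the reply also stand:

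- The protocol attaches the purpose of comparison to completion only. Satisfaction is reported for both groups. The interval for a difference follows text covering both rates, so a by-group reading of satisfaction is fair, but it is a reading.
- Every patient must meet the same device, connectivity and caregiver criteria (section 3.0). That narrows selection on ability to use a device, though not on travel distance, mobility or preference.
- The 30% in section 2.0 concerns missed appointments in the general clinic, not the completion measure of section 6.0. The 9:3 split was picked because it yields 0.30, and nothing in the documents makes it likely.
- Group 2 may be defined in consent material that is not in the text reviewed. The methods section would still need the rule.

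A reader might go further and infer that patients or staff do choose the group, so that the results will be biased. The documents do not support this. They are silent on the method, and silence does not show that allocation was uncontrolled. Nor do they support the inference that the feasibility conclusions fall. The MSTS criterion compares video with face-to-face scoring in the same patients, and the mobile group supplies both formats, so neither within-patient comparison depends on how the two groups were formed.

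**Conclusion.** The concern holds in a limited form. No allocation rule is stated for the 40 limited-efficacy patients, and the group label in section 5.0 does not match the design in section 4.0. The two measures that section 6.0 names for this phase, completion and satisfaction, are nevertheless reported by group, with an interval for the difference that covers sampling error only.

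The consequence is confined to reading those two between-group results. The bias has no size that can be derived from the documents. The sensitivity figure of 0.10 per exchange needs only 20 patients per group and a patient's completion status that does not depend on the group. The 9:3 example and its probabilities also need the assumed share of non-completers, and are an illustration rather than evidence of bias. The plan's sample size and precision figures are correct as stated.

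**What to change.** In section 4.0 (Specific Aim 3), state that after consent the 40 patients are randomised 1:1 to control or mobile surveillance from a concealed, computer-generated list, for example in REDCap, which the study already uses (section 7.0), and are analysed as randomised. Use the same group names in section 5.0, and remove or define group 2 for the feasibility phase.

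The cost is a short amendment, a randomisation list and the loss of any choice of group. Some patients may decline for that reason, and the documents give no figure for this. Sample size, visits and the 0.30 half-width do not change.

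If allocation must stay non-random, state the rule. Report by group the variables that section 8.0 already collects (demographics, type of cancer and surgical procedure), and present the between-group rates as descriptive and non-randomised. This needs no new data, but any difference would remain open to selection.
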